2. OBJECTIVES

2.1. Primary Objective

- To evaluate the effect of administration of neflamapimod (VX-745) for 24-weeks on immediate and delayed recall aspects of episodic memory, as assessed by the HVLT-R in subjects with mild AD.

2.2. Secondary Objectives

- To evaluate effects of neflamapimod on immediate and delayed recall of Logical Memory (LM), Verbal Paired Associates (VPA) and Visual Reproduction (VR) components of the WMS.
- To evaluate effects of neflamapimod on the CDR-Sum of Boxes (SB) and MMSE.
- To evaluate the effects of neflamapimod on AD-related CSF biomarkers (total tau, p-tau₁₈₁, A β ₁₋₄₀, A β ₁₋₄₂, neurogranin, and neurofilament light chain).

3. INVESTIGATIONAL PLAN

3.1. Overall Study Design and Plan

This is a Phase 2, multicenter, randomized, double-blind, placebo-controlled, proof-of-concept study of neflamapimod 40 mg or matching placebo administered twice daily for 24 weeks in subjects aged 55 to 85 years with CSF biomarker-confirmed AD; with global CDR score of 0.5 or 1.0, with CDR memory subscore of at least 0.5, and MMSE scores between 20 and 28, inclusive.

A schedule of assessments is presented in [Table 6-1](#).

3.1.1. Screening

Following completion of informed consent procedures, subjects will enter the Screening phase of the study.

Two screening visits are planned to allow most screening procedures to be completed and reviewed during the first visit before lumbar puncture to collect CSF to be performed on Screening Visit 2.

All screening assessments should be conducted within 42 days of Day 1 (first dose of study drug).

3.1.2. Treatment Period

Once eligibility is confirmed and before the first dose of study drug, subjects will be randomly assigned to receive neflamapimod or placebo; refer to [Section 5.4](#) for details regarding assignment to treatment group.

Dosing will start on Day 1, following completion of all Baseline procedures. During the treatment period, subjects will return to the clinic on Days 21, 42, 84, 126, and 168. Telephone contacts will be conducted to determine subject status and assess compliance between Days 42 and 84 (Visits 5 and 6); Days 84 to 126 (Visits 6 and 7); and Days 126 and 168 (Visits 7 and 8).

3.1.3. Follow Up

A Follow-up Visit will be conducted 14 (± 3) days following the last dose of study drug.

3.1.4. Early Discontinuation

Subjects who prematurely discontinue study drug for any reason will be asked to return to the clinical site for an Early Termination visit within 3 days following the last study drug dose; if it is determined that the subject will discontinue study drug while at the study center for a scheduled visit, then the Early Termination visit should be conducted at that time. These subjects will also be asked to return to the clinical site for a Follow-up Visit 14 (± 3) days following the last study drug dose.

Every effort should be made to ensure a subject returns for this visit.

Refer to [Section 4.3](#) for details regarding removal of subjects from treatment.

3.2. Discussion of Study Design

The primary objective of assessing episodic memory was chosen to provide a robust assessment of the potential of neflamapimod to reverse hippocampal dysfunction in subjects with mild AD. Defects in episodic memory are a defining characteristic of AD and is one of earliest manifestations of cognitive

dysfunction in the disease process (Gold & Budson, 2008; Tromp et al, 2015). In addition, neflamapimod demonstrated effects on episodic memory in the Phase 2a studies.

The HVLt-R test was chosen as the assessment tool for the primary endpoint because it has alternative versions validated in multiple cultural and language contexts, has high test-retest reliability, and shows good short-term stability (i.e., no practice effects) in subjects with mild AD (Phillips et al, 2012).

3.2.1. Rationale for Dose Selection

The dosing regimen of 40 twice daily for 24 weeks is based on available efficacy (pharmacological activity; Section 3.2.1.1) and safety (Section 3.2.1.2) data.

3.2.1.1. Efficacy Considerations

The 40 mg BID regimen was chosen because PK-PD modeling (plasma drug concentration response) correlations indicated a plasma drug concentration dependency on the effects on episodic memory that argues against going to lower doses and only modest further increase in efficacy with utilizing 125 mg dose level, while the loss of an amyloid plaque load effect at 125 mg dose level provides a specific reason not to increase the dose above 40 mg. The PK-PD modeling was also consistent with the *in vitro* potency of the drug and predicted doses for optimal cognitive effects based on pre-clinical studies (Alam, 2015). Moreover, the 40 mg dose level provides an appropriate safety margin relative to findings in chronic toxicology findings in the dog (Section 3.2.1.2).

3.2.1.2. Safety Considerations

Based on the clinical experience to date at higher doses and the results from animal toxicology studies, the neflamapimod dose of 40 mg BID and lower is expected to be well tolerated and to have a low risk of drug toxicity.

In the Phase 2a studies (Study 303) of 6- or 12-weeks neflamapimod dosing in patients with mild AD, a total of 25 subjects were enrolled. With regard to safety, neflamapimod was well tolerated, with 24 of 25 subjects completing their scheduled dosing period (8 completed 6 weeks neflamapimod administration, and 16 completing 12 weeks neflamapimod administration). The one subject who discontinued early did so within the first week of study drug administration due to an adverse event (AE) of vomiting, attributed primarily to persistent CSF leakage after the predose/baseline CSF collection. There were no severe or serious AEs reported. The most common AEs across the 2 studies were mild somnolence (sleepiness or drowsiness) reported in 5 patients, and self-limited mild diarrhea (loose stools) reported in 4 patients. There was also one event of moderate diarrhea, which was considered not related, as the event did not recur during additional 8 weeks of treatment after having resolved during a brief treatment interruption. No treatment-related or clinically relevant trends in the analysis of safety laboratory and 12-lead electrocardiogram (ECG) parameters were observed. More specifically, there were no abnormalities in liver function tests (LFTs), nor any trends in changes in LFT parameters, noted in either study. LFT abnormalities, specifically increases in liver transaminases, were seen in 10% to 15% of patients in a prior study in patients with RA at a dose of 250 mg BID for 3 months. Due to the use of different formulations in the RA studies, the plasma drug concentrations were 4- to 5-fold higher than in the Phase 2a mild AD studies.

The 40 mg BID dose level provides a 5-fold margin based on plasma drug levels to no adverse effect level and 10-fold margin to minimal and/or equivocal findings for hematological, hepatic and

neuropathological changes in chronic (9- and 12-month) dog toxicology studies. Further details are provided in the investigator brochure.

4. SELECTION OF STUDY POPULATION

4.1. Inclusion Criteria

Subjects meeting all of the following criteria are eligible for enrollment in this study:

1. Men and women age 55 to 85 years, inclusive.
2. Willing and able to provide informed consent.
3. Must have MCI or mild AD with evidence of progression (“Mild-AD”), as defined by the following:
 - a. CDR-Global Score of 0.5 or 1.0, with CDR memory subscore of at least 0.5.
 - b. MMSE score ranging from 20 to 28, inclusive.
 - c. Positive biomarker for AD, as defined by a CSF A β ₁₋₄₂ below the threshold and phospho-tau above the threshold for the assay utilized in the study and assessed by the central laboratory.
4. Computed tomography (CT) or magnetic resonance imaging (MRI) findings within 2 years of Screening that are compatible with AD (i.e., no other pathologic processes that would account for the cognitive deficit).
5. If the subject is taking a single drug for AD (e.g., donepezil or other cholinesterase inhibitors or memantine; dual therapy is excluded), he/she has been on a stable dose for at least 2 months prior to baseline, and the dose must remain unchanged during the study unless required for management of AEs.
6. Adequate visual and auditory abilities to perform all aspects of the cognitive and functional assessments.
7. Must have reliable informant or caregiver. In Czech Republic only, the caregiver must be either sharing the same household as the subject or be in personal contact with the subject at least 5 days per week.

4.2. Exclusion Criteria

Subjects meeting any of the following criteria are not eligible for enrollment in this study:

1. Evidence that the primary basis for cognitive impairment is neurodegenerative disease other than AD, including, but not limited to, vascular dementia, dementia with Lewy bodies, and Parkinson’s disease.
2. Suicidality, defined as active suicidal thoughts within 6 months before Screening or at Baseline, defined as answering yes to items 4 or 5 on the Columbia-Suicide Severity Rating Scale (C-SSRS), or history of suicide attempt in previous 2 years, or, in the Investigator’s opinion, at serious risk of suicide.
3. History of major and active psychiatric disorder, moderate to severe depressive symptoms, and or other concurrent medical condition that, in the opinion of the Investigator, might compromise safety and/or compliance with study requirements.
4. Diagnosis of alcohol or drug abuse within the previous 2 years.

5. History of cancer within the last 5 years, except basal cell carcinoma, squamous skin carcinoma, prostate cancer or carcinoma in situ with no significant progression over the past 2 years.
6. Poorly controlled clinically significant medical illness, such as hypertension (blood pressure >180 mmHg systolic or 100 mmHg diastolic); myocardial infarction within 6 months; uncompensated congestive heart failure or other significant cardiovascular, pulmonary, renal, liver, infectious disease, immune disorder, or metabolic/endocrine disorders or other disease that would preclude treatment with p38 mitogen activated protein (MAP) kinase inhibitor and/or assessment of drug safety and efficacy.
7. History of serum B12 abnormality, anemia with hemoglobin ≤ 10 g/dL, thyroid function abnormality, electrolyte abnormality, or positive syphilis serology that have not been corrected and/or otherwise addressed.
8. History of epilepsy or unexplained seizure within the past 5 years.
9. Aspartate aminotransferase (AST) or alanine aminotransferase (ALT) $> 2.5 \times$ the upper limit of normal (ULN), total bilirubin $> 1.5 \times$ ULN, and/or International Normalized Ratio (INR) > 1.5 .
10. Known human immunodeficiency virus or active hepatitis B or hepatitis C virus infection.
11. Subject participated in a study of an investigational drug less than 3 months or 5 half-lives of the investigation drug, whichever is longer, before enrollment in this study.
12. Male subjects with female partners of child-bearing potential who are unwilling or unable to adhere to contraception requirements ([Section 5.8](#))
13. Female subjects who have not reached menopause or have not had a hysterectomy or bilateral oophorectomy/salpingo-oophorectomy.
 - If a female subject reached menopause within the previous year, a pregnancy test must be performed during Screening and the subject must be willing to adhere to the contraception requirements specified in the protocol. Such subjects with a positive urine or serum pregnancy test are not eligible for study participation.
14. Requires concomitant use of strong cytochrome P450 (CYP) 3A4 inhibitors or anti-tumor necrosis factor-alpha therapies during study participation (see [Section 5.7](#)).

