5.7. Prior and Concomitant Therapy

Any medications taken from Screening through Follow-up Visit, including all prescription and over-the-counter medications as well as supplements, will be documented in the subject's source document and in the eCRF.

At study entry, any subject taking a drug for AD (e.g., donepezil or other cholinesterase inhibitors or memantine) must have been on a stable dose for at least 2 months (refer to [Section 4](#)). Furthermore, the dose must remain unchanged during the study, unless required for management of AEs.

While drug-drug interaction studies have not been conducted, in vitro testing indicates that neflamapimod is metabolized by oxidation in the liver by the CYP system (combination of CYP3A4 and CYP2C19 isozymes). Until the metabolism is better characterized, **concomitant strong inhibitors of CYP3A4 are prohibited and strong inducers of CYP3A4 should be used with caution in subjects receiving neflamapimod**, as the use of such drugs in could impact neflamapimod metabolism in subjects who have an underlying CYP2C19 genotypic variant that impacts activity of that CYP2C19. Subjects will be tested for CYP2C19 genotype at baseline to assess any differences in neflamapimod levels and effect (see [Section 6.2.5](#)).

The following medications are prohibited during study participation:

- Strong CYP3A4 inhibitors (see [Table 5-1](#)).
- Any other investigational drug. If a subject has previously participated in a study of an investigational drug, last dosing must have occurred 3 months or 5 half-lives of the investigation drug, whichever is longer, before enrollment in this study.
- Any anti-tumor necrosis factor-alpha therapy.
- Typical and atypical antipsychotics.

The Medical Monitor should be contacted with any questions regarding concomitant use of medications that are thought to modulate CYP3A4 activity.

Table 5-1: CYP3A4 Inhibitors

Strong Inhibitors ≥5-fold increase in AUC or >80% decrease in CL	Moderate inhibitors ≥2 but <5-fold increase in AUC or 50-80% decrease in CL	Weak inhibitors ≥1.25 but <2-fold increase in AUC or 20-50% decrease in CL

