6.2.5. Genotyping and Apolipoprotein E4 Testing

A blood sample will be collected from all subjects at Visit 3 (Day 1) for CYP2C19 genotyping; such testing is mandatory. The CYP2C19 gene encodes for a drug metabolizing enzyme that accounts for approximately half the metabolism of neflamapimod. (The other is the CYP3A4 enzyme). As there are known polymorphisms in CYP2C19, particularly in Asian populations, that reduce the function of this enzyme, the PK profiles in individual subjects may be impacted CYP2C19 genotype (Fricke-Galindo et al, 2016). PK profiles will be obtained in all subjects and correlated against CYP2C19 genotype (see Section 6.2.8 and Section 8.4). An aliquot of blood from this sample may also be used for measurement of apolipoprotein E4; such testing is optional. Results will be available to study sites and may be discussed with the subjects only after the clinical study report has been completed.

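### Section 5.7 leaves moderate CYP3A4 inhibitors to optional consultation, although in a CYP2C19 poor metaboliser one could, on stated assumptions, take exposure past the protocol's 5-fold margin

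*Protocol*

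**What the plan says.** Exclusion 14 (Protocol Section 4.2, repeated in the Synopsis) bars a subject who "Requires concomitant use of strong cytochrome P450 (CYP) 3A4 inhibitors or anti-tumor necrosis factor-alpha therapies during study participation".

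Section 5.7 gives the treatment-period rule: "concomitant strong inhibitors of CYP3A4 are prohibited and strong inducers of CYP3A4 should be used with caution in subjects receiving neflamapimod". It gives the reason too: "as the use of such drugs in could impact neflamapimod metabolism in subjects who have an underlying CYP2C19 genotypic variant". No drug-interaction study has been done; the metabolic picture is that "in vitro testing indicates that neflamapimod is metabolized by oxidation in the liver by the CYP system (combination of CYP3A4 and CYP2C19 isozymes". Section 6.2.5 adds the proportions: "The CYP2C19 gene encodes for a drug metabolizing enzyme that accounts for approximately half the metabolism of neflamapimod", with CYP3A4 named as the other enzyme.

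Table 5-1 defines a middle class, "Moderate inhibitors ≥2 but <5-fold increase in AUC or 50-80% decrease in CL", and lists drugs such as verapamil, ciprofloxacin, erythromycin and fluconazole. The prohibited list does not include this class. The one provision that reaches it is general: "The Medical Monitor should be contacted with any questions regarding concomitant use of medications that are thought to modulate CYP3A4 activity".

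Section 3.2.1.2 supports the dose with an exposure margin: "The 40 mg BID dose level provides a 5-fold margin based on plasma drug levels to no adverse effect level and 10-fold margin". The second figure refers to changes in 9- and 12-month dog studies that the protocol describes as minimal or equivocal.

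**The concern.** The stated reason for the restriction reaches further than the restriction does. If CYP2C19 and CYP3A4 each carry about half of clearance, a subject with normal CYP2C19 reaches at most 2-fold exposure even when CYP3A4 is fully blocked (1/0.5). So on the protocol's own split, the CYP3A4 rule matters for the 5-fold margin mainly when CYP2C19 is deficient. In that subject a moderate inhibitor also acts on the main remaining route.

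Nobody has to review the combination before it starts. Genotype is sampled on Day 1 (Section 6.2.5) and is not an eligibility criterion. No section gives it to the Medical Monitor during the trial. The 3-monthly pharmacokinetic review in Section 8.7 sees genotype, but neither co-medication nor subject identity. Section 5.6 allows no dose reduction.

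What is at stake is the safety of a few subjects. The effect on the primary analysis is negligible. Section 3.2.1.2 also reports raised transaminases in 10% to 15% of rheumatoid arthritis patients on 250 mg BID for 3 months, at concentrations 4- to 5-fold above the Phase 2a Alzheimer's studies.

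**Working it through.** **Figures that can be reproduced.** The bands in Table 5-1 agree with AUC ratio = 1/(1 − i), where i is the fractional loss of clearance: i = 0.5 gives 2 and i = 0.8 gives 5. The 5-fold margin cannot be recomputed, because the details are in the investigator brochure. It is taken as stated.

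**Inputs from the protocol.** CYP2C19 about 0.5 and CYP3A4 about 0.5 of metabolism (Section 6.2.5); i from 0.5 to 0.8 for the moderate class (Table 5-1), read as loss of CYP3A4 clearance; a 5-fold margin (Section 3.2.1.2).

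**Assumed.** Residual CYP2C19 activity a (1 = normal, 0 = none) and a third clearance route t. Neither is in the documents.

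**Model.** Relative clearance = (1 − t) × [0.5a + 0.5(1 − i)] + t. Exposure ratio (AUC) = 1/relative clearance.

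| Case | i = 0.5 | i = 0.8 |
|---|---|---|
| Normal CYP2C19 (a = 1, t = 0) | 1/0.75 = 1.33 | 1/0.60 = 1.67 |
| Poor metaboliser, base case (a = 0, t = 0) | 1/0.25 = 4.0 | 1/0.10 = 10 |
| a = 0.10, t = 0 | 1/0.30 = 3.33 | 1/0.15 = 6.67 |
| a = 0.20, t = 0 | 1/0.35 = 2.86 | 1/0.20 = 5.0 |
| a = 0.50, t = 0 | 1/0.50 = 2.0 | 1/0.35 = 2.86 |

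A poor metaboliser with no inhibitor is at 1/0.5 = 2-fold. The 10 is an open upper bound, since the class ends below 5-fold AUC.

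**Where 5-fold is passed.** In the base case, 0.5(1 − i) < 0.20 requires i > 0.60.

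**How much third route removes it at i = 0.8.** Break-even t = (0.20 − c)/(1 − c), with c = 0.5a + 0.1. For a = 0, 0.05, 0.10, 0.15 and 0.20 this gives 11.1%, 8.6%, 5.9%, 3.0% and 0. As a check, a = 0.10 with t = 0.06 gives 0.94 × 0.15 + 0.06 = 0.201, or 4.98-fold.

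**Varying the split (a = 0).** With a CYP3A4 share of 0.4 the moderate band gives 1/0.20 = 5.0 to 1/0.08 = 12.5. With 0.6 it gives 1/0.30 = 3.3 to 1/0.12 = 8.3. With 0.6 and a 10% third route it gives 1/(0.54 × 0.5 + 0.1) = 2.7 to 1/(0.54 × 0.2 + 0.1) = 4.8, with no breach.

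**Frequency.** Assume 2% to 15% poor metabolisers and 2% to 10% use of moderate inhibitors, independent of each other.
- Co-exposed on active drug: 76 × 0.02 × 0.02 = 0.03 to 76 × 0.15 × 0.10 = 1.14. The chance of at least one is 1 − (1 − 0.0004)^76 = 3% to 1 − (1 − 0.015)^76 = 68%.
- Passing 5-fold, with inhibition assumed evenly spread over 50% to 80%: in the base case (0.80 − 0.60)/0.30 = 2/3 of these, so 0.02 to 0.76 subjects (2% to 53% chance of at least one). With a = 0.10, 1/3 of these, so 0.01 to 0.38 subjects (1% to 32%). With a = 0.10 and t = 0.06, none.

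**The case against.** The case against has weight.

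- **The breach is fragile.** It needs near-zero CYP2C19 activity, little other clearance and inhibition above 60%. The half/half split is approximate and in vitro, and Table 5-1 gives a class range, not a value per drug. This stands.
- **The metric may not match.** The model gives an AUC ratio; the margin is stated on plasma drug levels, with no metric named. If it is on peak concentration, lower clearance would usually raise the peak by less than the AUC. This stands and cannot be settled from the documents.
- **The consequence is limited.** Even 10-fold corresponds to minimal and/or equivocal findings in long dog studies, and the excess lasts only as long as the co-medication. Phase 2a showed no liver-test abnormalities. Chemistry is scheduled repeatedly, Section 4.3 has mandatory liver stopping rules, exclusions 3 and 6 allow Investigator judgement, and co-medication is recorded at each visit. All true, but these do not require review of the combination before it starts.
- **The class is already covered.** The Medical Monitor sentence takes in every CYP3A4 modulator, so the class is not ignored. But contact depends on someone having a question.
- **Approval alone would not help.** Only poor metabolisers are at risk. Without genotype the Medical Monitor would have to approve blindly or refuse everyone. This is right, and the fix has to supply the genotype.

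A reader might infer that the plan permits a combination known to exceed the safety margin, or that subjects would be harmed. The documents support neither. The 4- to 10-fold range is a model result, and passing a no-adverse-effect level is not a toxicity finding. The rheumatoid arthritis ratio is to Phase 2a levels at 40 and 125 mg together. Section 1.3 calls the difference between those doses insubstantial. If 125 mg did give more, the multiple over 40 mg would be above 4 to 5.

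**Conclusion.** The gap is real but narrow. The protocol restricts CYP3A4 inhibitors because of CYP2C19 variants, and leaves the moderate class to optional consultation. On its own approximate split, that class could carry a poor metaboliser past 5-fold.

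The conclusion rests on almost no residual CYP2C19 activity, almost no third route, inhibition in the upper two-thirds of the moderate band, and a margin that can be compared with AUC. Relaxing these modestly removes the breach. On assumed rates about one subject at most would be co-exposed, and fewer would pass 5-fold.

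This is a cheap safety improvement, between optional and a low-priority recommendation. It is not grounds for a full bar on moderate inhibitors or for changing eligibility: in subjects with normal CYP2C19 the same drugs give at most 1.67-fold.

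**What to change.** Add to Protocol Section 5.7, after the prohibited list:

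*Moderate CYP3A4 inhibitors (Table 5-1) may be used only with prior approval of the Medical Monitor, who will have access to the subject's CYP2C19 genotype (not treatment assignment). They should not be combined with study drug in CYP2C19 poor metabolisers, or while genotype is unknown, unless no suitable alternative exists. Urgent treatment must not be delayed; in that case notify the Medical Monitor within 24 hours and check liver tests.*

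The urgent-treatment clause is needed because several listed drugs are anti-infectives. The genotype is already collected and does not reveal the arm. With moderate inhibitors kept out of poor metabolisers, the worst remaining case in the base model is a weak inhibitor: 1/(0.5 × 0.8) = 2.5-fold to 1/(0.5 × 0.5) = 4-fold. With a CYP3A4 share of 0.4, the edge of the weak band would just reach 1/(0.4 × 0.5) = 5.0-fold.

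Cost: on the assumed use, 152 × 0.02 = 3 to 152 × 0.10 = 15 requests across both arms, about half from placebo subjects, and more with repeat courses. Some co-medications would be substituted. Since no dose reduction is allowed, an occasional subject may have to stop study drug. For a subject already on a moderate inhibitor at entry, the Day 1 genotype sample comes too late to guide the first dose, so the Medical Monitor would need to settle the matter during screening. Exclusion 14 and the SAP stay as they are.
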